11 STATISTICAL METHODOLOGY

11.1 General

Data listings will be provided for the ITT Population. Summary statistics and statistical analyses will be performed for patients included in the relevant analysis populations.

For continuous data, summary statistics will include the arithmetic mean, arithmetic standard deviation, median, minimum, maximum, and number. For log-normal data (eg, the PK parameters: AUCs and maximum observed concentration [C_{max}]), the geometric mean and geometric coefficient of variation (CV%) will also be presented. For categorical data (i.e. ST-segment resolution and persistent arrhythmias), frequency counts, percentages and odds ratios will be presented, where applicable. Data listings will be provided for all patients up to the point of withdrawal, with any patients excluded from the relevant population highlighted. For the calculation of summary statistics and statistical analysis, unrounded data will be used.

Missing values will not be imputed.

Data analysis will be performed using SAS® Version 9.4 or higher.

Analysis Data Model (ADaM) datasets will be prepared using Clinical Data Interchange Standards Consortium (CDISC) ADaM Version 2.1, and CDISC ADaM Implementation Guide Version 1.1. Pinnacle 21 Community Validator Version 2.1.2 will be utilized to ensure compliance with CDISC standards.

11.1.1 Definition of Baseline and Change from Baseline

Baseline for each parameter is defined as the last value measured prior to dosing, including repeat vital signs and unscheduled (clinical laboratory parameters) readings (see Section [11.1.2](#) for definitions of repeat and unscheduled readings).

Mean change from baseline is the mean of all individual patients' change from baseline values. Each individual change from baseline will be calculated by subtracting the individual patient's baseline value from the value at the timepoint. The individual patient's change from baseline values will be used to calculate the mean change from baseline using a SAS procedure such as Proc Univariate.

11.1.2 Repeat and Unscheduled Readings

Repeat readings are labelled as ‘Repeat’ in the listings and replace the original readings in all summaries and changes from baseline presentations and calculations. Prior to dosing, all readings taken in addition to the original reading are defined as predose repeats. Postdose repeat readings are defined as readings collected within 15 minutes of the actual time of the original reading.

All results not taken at a scheduled timepoint for other data types (eg, clinical laboratory parameters) are unscheduled. Unscheduled readings are labelled as ‘Unscheduled’ in the listings. Because unscheduled readings are not associated with any scheduled timepoint, they are excluded from all summaries (with the exception that they may be used as baseline, as stated in Section 11.1.1).

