5.5.2 Treatment Day 1 – in Cardiac Catheterization Lab and Recovery

- Random allocation to study drug (once screening is complete and consent is obtained either from the subject or a legally authorized representative of the subject, randomization must occur to ensure study drug is given by bolus injection between an hour prior to and 5 minutes prior to coronary reperfusion, so as to be complete at least 5 minutes prior to reperfusion)
- Study drug administration
- Vital signs (pulse, respiratory rate, blood pressure) will be recorded every 15 minutes after study drug for an hour, then hourly for another 4 hours. There is a +/- 10 minute window on all vital sign collections
- Blood sampling to assess anticoagulation during the procedure (INR)
- Documentation of peri-procedural arrhythmias by medical staff by 12-lead ECG
- Continuous ECG monitoring will commence post procedure as soon as the 7 day wearable device can be affixed to the patient and up to 14 days post study drug¹
- Standard 12 lead ECG prior to treatment to obtain baseline ST-segment elevation and again at 4 hours post-study drug to assess ST segment resolution (3 strips at each time point)
- Blood samples for troponin T will be obtained (see time points in Section 12)
- PK blood sampling (see time points in Section 12)
- Blood sample to assess biomarkers of cardiac injury and inflammation (see time points in Section 12)
- Laboratory safety tests (as outlined in Section 12)
- Recording of concomitant medications
- Recording of any AEs
- If study informed consent was given by the subject's legally authorized representative for study enrollment, the subject will be provided with a modified consent once they are stable (after investigational drug treatment and STEMI procedure) and

in the opinion of the investigator capable of providing written consent. This modified informed consent document will cover the subject's agreement to remain in the clinical trial and proceed with all study related procedures and follow-up.

¹ The wearable ECG monitor device should be affixed to the patient as soon as possible post-study drug. This single-use device will need to be removed when the patient undergoes CMR at 72 +/- 24 hours post-study drug. At that time, a new wearable ECG monitor device will need to be affixed to the patient.

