10. Vital signs (pulse, respiratory rate, blood pressure) will be recorded every 15 minutes after study drug for an hour, then hourly for another 4 hours. There is a +/- 10 minute window on all vital sign collections
11. 12-lead ECG for day 1: at screening for diagnosis of STEMI for inclusion criteria, and to obtain baseline ST-segment elevation, during PCI treatment to document peri-procedural arrhythmias and again at 4 hours post study drug for ST-segment resolution. 3 strips each at screening and 4 hour time point
12. 12-lead ECG including rhythm strip to identify any persistent arrhythmias
13. 12-lead ECG including rhythm strip to identify any persistent arrhythmias
14. Prior to study enrollment written informed consent will be obtained either from the subject or a legally authorized representative of the subject. If study informed consent was given by the subject's legally authorized representative prior to study enrollment, the subject will be provided with a modified consent once they are stable (after investigational drug treatment and STEMI procedure) and in the opinion of the investigator capable of providing written consent. This modified informed consent document will cover the subject's agreement to remain in the clinical trial and proceed with all study related procedures and follow-up.

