11.5.3 Vital Signs

Vital signs values outside the clinical reference ranges will be flagged on the individual patient data listings.

The vital signs data will be summarized by treatment group, together with changes from baseline. Figures of mean vital signs and mean change from baseline profiles will be presented by treatment. Repeat and unscheduled readings will be handled as defined in Section [11.1.2](#).

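### The SAP's time-only definition of a repeat cannot separate a repeat vital sign from the next scheduled one in the first hour after dosing, so scheduled values can be displaced if it is programmed as written

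*SAP*

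**What the plan says.** SAP 11.1.2 sets one criterion for a postdose repeat: "Postdose repeat readings are defined as readings collected within 15 minutes of the actual time of the original reading". It asks for no shared nominal timepoint and no repeat mark on the case report form, and it does not exempt scheduled readings. Repeats "replace the original readings in all summaries and changes from baseline presentations and calculations". SAP 11.5.3 brings vital signs under this rule: "Repeat and unscheduled readings will be handled as defined in Section" 11.1.2.

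Protocol 5.5.2 says that vital signs "will be recorded every 15 minutes after study drug for an hour, then hourly for another 4 hours". The same section and footnote 10 to Table 2 add: "There is a +/- 10 minute window on all vital sign collections".

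For other data types, such as laboratory parameters, SAP 11.1.2 says: "Because unscheduled readings are not associated with any scheduled timepoint, they are excluded from all summaries". The one exception is use as baseline.

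Replaced values are not deleted. SAP 11.1.2 states: "Repeat readings are labelled as ‘Repeat’ in the listings". SAP 11.5.3 flags out-of-range vital signs in the listings, and SAP 11.5.2 lists out-of-range laboratory values by parameter and treatment.

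**The concern.** The repeat window and the first-hour sampling interval are the same length, 15 minutes. A scheduled reading taken a little early, or one that follows a late reading, therefore meets the SAP's definition of a repeat of the reading before it. Applied literally, the 30-minute value would stand in for the 15-minute value, and so on. The SAP does not say what the later timepoint would then show.

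The first hour after the bolus is the most densely sampled vital-sign period in the protocol and the only one exposed to this problem. SAP section 9 calls this the first study in patients, with safety as its main focus. SAP 11.5.6 plans no safety inference, so the descriptive tables and figures carry the group comparison for vital signs.

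A second issue does not depend on how the rule is programmed. A genuine repeat removes its original from the group summaries, and an unscheduled postdose laboratory result enters no summary, including the shift tables. No table of worst postdose values is specified to bring these readings back.

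**Working it through.** The plan states no figure here to reproduce. The check sets the repeat rule against the schedule.

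**Inputs**
- Repeat window: 15 minutes from the actual time of the original (SAP 11.1.2).
- Schedule, read as 15, 30, 45 and 60 minutes, then 120, 180, 240 and 300 minutes (Protocol 5.5.2).
- Collection window: 10 minutes either side (Protocol 5.5.2; Table 2, footnote 10).
- Assumption: timing errors e1 to e4 of the first-hour readings are independent and identically distributed. The documents give no data on timing.

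**1. Permitted gaps.** With half-width w, consecutive first-hour readings lie 15 - 2w to 15 + 2w minutes apart. For w = 10 this is -5 to +35 minutes. From 60 minutes on, the smallest gap is 60 - 20 = 40 minutes, so the hourly readings never meet the rule.

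**2. Share of pairs that qualify.** The gap is 15 + e(i+1) - e(i). It is 15 or less exactly when e(i+1) is no larger than e(i), which has probability 1/2 by symmetry. Simulation with uniform errors gave 0.501, 0.500 and 0.502 for w = 10, 5 and 2. Tighter timing does not lower this share while any random error remains.

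**3. Patients with at least one such pair.** All three gaps exceed 15 only if e1 < e2 < e3 < e4, which is one of 4! = 24 equally likely orders. So 1 - 1/24 = 23/24 = 95.8% have at least one. Simulation gave 95.8% to 95.9%.

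**4. Readings displaced per patient under literal programming.**
- If a repeat can itself be replaced, each short gap displaces one reading: 3 x 1/2 = 1.5 (simulation 1.49 to 1.51).
- If it cannot, count the 24 orders. One gives no short gap. Six displace two readings (five with gaps short-long-short, one with all three short). The other 17 displace one. The mean is (17 + 2 x 6)/24 = 29/24 = 1.21. This holds while readings two apart stay more than 15 minutes apart, that is 30 - 2w > 15, or w < 7.5. Simulation gave 1.20 and 1.21 for w = 2 and 5, and 1.26 for w = 10.

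**5. Exact timing.** Every gap is then exactly 15 minutes. If the limit includes 15, 2 of the 4 first-hour readings are displaced, or 3 of 4 if repeats can be replaced. If it means under 15, none are.

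**6. Timepoint-based definition.** If a repeat must share the nominal timepoint of its original, 0 of the 4 scheduled readings can be displaced by another scheduled reading, whatever the timing.

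**The case against.** The strongest reply is that the SAP does not intend a scheduled reading to count as a repeat. It speaks of a repeat of an original, its predose sentence describes repeats as extra readings, and SAP 11.1.1 takes change from baseline at each timepoint. A programmer who works by nominal timepoint or by a repeat mark on the case report form would overwrite nothing scheduled. The table shells named in SAP section 4 might settle it, but they are not among the documents. This reading is plausible, so displacement is a risk and not a certainty. But SAP 11.1.2 does not state it, and the definition is tied to actual time, which points a programmer the other way.

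A reader might infer that first-hour values are bound to be overwritten, that abnormal readings disappear, and that the group comparison is pulled toward normal. The documents do not support this.
- Overwriting needs time-only programming.
- Replaced values stay in the listings, with repeats labelled and out-of-range values flagged.
- SAP 11.1 plans median, minimum and maximum as well as means, although these would be taken after any replacement.
- A haemodynamic change or laboratory abnormality judged adverse also reaches the group tables as an adverse event (Protocol 13.1, SAP 11.5.1).
- Replacing one scheduled reading with the next does not depend on its value, so it has no inherent direction. A pull toward normal could arise only from genuine repeats prompted by abnormal readings. The documents set no trigger for repeats and give no blood pressure distribution, so no size can be put on it.

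It is also fair to object to keeping originals in the postdose means. SAP 11.1.1 lets baseline use repeats, so different rules before and after dosing could distort change from baseline. That objection stands, and the fix does not require such a change.

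**Conclusion.** The point holds as a fault in a stated rule. As written, SAP 11.1.2 cannot tell a repeat from the next scheduled reading in the first hour. Under literal programming and independent, identically distributed timing errors, about 50% of consecutive first-hour pairs qualify, about 96% of patients have at least one such pair, and 1.2 to 1.3 readings per patient are displaced (1.5 with chained replacement). The 96% is the share of patients who lose a value only under that programming. With exact timing, the result turns on whether the 15-minute limit is inclusive.

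The reach is narrow: descriptive first-hour vital-sign summaries. The hourly readings, the arrhythmia outcome and every hypothesis test are unaffected.

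The loss of replaced originals and unscheduled laboratory results from the group summaries holds under either programming. It concerns summaries only, and its size is unknown. The sponsor should make the change, because descriptive safety tables matter in this study and the correction is nearly free.

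**What to change.** In SAP 11.1.2, define a postdose repeat as an additional reading recorded for the same nominal timepoint as its original, and state that a scheduled reading is never a repeat of another scheduled reading.

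In SAP 11.5.2 and 11.5.3, add by-group tables of the worst postdose vital sign and the worst post-baseline laboratory shift. Both should use all readings, including replaced originals and unscheduled results.

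Changing which reading enters the by-timepoint means is optional. The baseline rule can stay.

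The cost is one sentence of SAP wording and a few extra tables, with no new data and no added patients.

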11.2 Demographics, Patient Disposition, and Baseline Characteristic

The demographic variables age, sex, race, ethnicity, body weight, height, and body mass index will be summarized and listed. Patient disposition will be summarized and listed.

Selected details from the primary PCI procedure will be summarized and all data will be listed.

Medical history will be summarized by Medical Dictionary for Regulatory Activities (MedDRA) system organ class and preferred term for each treatment group, respectively. This data will also be listed.

Important and non-important protocol deviations and the patient assignment to analysis populations will be listed.

11.3 Previous and Concomitant Medications

Any medication which started and ended prior to the start of study drug dosing will be considered as a previous medication. Concomitant medications are medications that are present before the study drug dosing but which were either stopped after the study drug dosing, or ongoing during study and medications that were started on or after the study drug administration.

The previous and concomitant medications will be summarized by preferred term and World Health Organization (WHO) Anatomical Therapeutic Chemical (ATC) codes for each treatment group. Primary PCI medications will not be coded or summarized.

All previous and concomitant medications (including primary PCI medications) will be listed.

11.4 Safety and Efficacy Assessment

All analyses under this section will be performed using the ITT population and also repeated with the PP population.

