6.2 Subject Exclusion Criteria

1. Previous myocardial infarction
2. Left bundle branch block (LBBB)
3. Previous coronary artery bypass graft surgery (CABG)
4. Major hemodynamic instability or uncontrolled ventricular arrhythmias.
5. Known contraindication to CMR (e.g. pacemaker)
6. Patients with known thyroid disease, or known allergy to iodide.
7. Subjects with past or current renal impairment requiring dialysis
8. Pregnant or females of child bearing potential
9. Body weight > 120 kg or Body Mass Index (BMI) > 35 kg/m²
10. Use of investigational drugs or devices within 30 days prior to enrollment into the study.
11. Life expectancy of less than 1 year due to non-cardiac pathology
12. Any clinically significant abnormality identified at the time of screening that in the judgment of the Investigator or any sub-Investigator would preclude safe completion of the study

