14.1.6 General Analysis of Safety and Efficacy Outcomes

Analysis of the primary safety outcome: characterize the number and incidence rate of serious arrhythmias that occur during a 14-day interval in this patient population. No hypothesis will be tested and data will be descriptive in nature only. A more detailed analysis strategy will be outlined in the SAP.

Analysis of exploratory secondary efficacy outcomes: For all variables with a continuous outcome including infarct size relative to the VV, MSI, absolute MI size, cardiac function, biomarkers of cardiac injury and cardiac troponin levels, a single pairwise comparison to analyze differences between all three FDY-5301 groups (combined) and placebo will be used. An unpaired Student's T test will be used for the pairwise comparison if the data are normally distributed and a Mann-Whitney rank test will be used for nonparametric data. Each group will then be tested using a one-way analysis of variance (ANOVA) to obtain a common variance followed by a Dunnett's post-test to separately compare each FDY-5301 dose group to placebo.

For categorical outcome including ST-segment resolution and incidence of all-cause and cardiac related mortality or morbidity, odds ratios comparing each FDY-5301 treatment group with placebo will be calculated.

Physical examination data from baseline, post-study and **medical history** data at baseline and peri-procedural arrhythmia data will be listed by patient. All clinical safety and tolerability data will be listed for each subject. **Laboratory values** will be calculated as group mean data and presented in shift tables. Comments as to the clinical significance of out of range values will be listed separately. **Adverse event** data will be summarized by group, visit, severity, and possible relationship to the study drug.

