10 DEFINITION OF ANALYSIS POPULATIONS

The **Intent-to-treat (ITT)** population will include patients who gave assent, full consent, abbreviated consent or waived consent and were randomized. This is the “full analysis set” of patients. Patients are included in the ITT population according to the treatment assigned.

The **Safety Population** will consist of all patients who received at least 1 dose of study drug (FDY-5301 or Placebo) and have at least 1 postdose safety assessment.

The **Per Protocol (PP)** population will be a subset of the ITT population and will include patients who gave informed assent/consent, were randomized, received any amount of study drug, underwent PCI, and underwent magnetic resonance imaging (MRI) at 72 ± 24 hours and 3 months.

The **PK Population** will consist of all subjects dosed with FDY-5301 and have at least 1 quantifiable postdose PK concentration.

The **PK/PP Population** will consist of all subjects who satisfy the criteria for both the PK and PP population.

All protocol deviations that occur during the study will be considered prior to database lock for their severity/impact and will be taken into consideration when patients are assigned to analysis populations. Details of patient assignment to the analysis populations will be listed.

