11.5 Safety and Tolerability Assessments

All safety analyses will be performed with the safety population.

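### The per-protocol repeat of the 14-day arrhythmia analyses makes a day-14 safety outcome depend on completing a 3-month MRI, and the Safety population is not named for that outcome

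*SAP*

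**What the plan says.** Protocol 14.1.6 treats arrhythmia as a safety outcome: "Analysis of the primary safety outcome: characterize the number and incidence rate of serious arrhythmias that occur during a 14-day interval in this patient population". It adds: "No hypothesis will be tested and data will be descriptive in nature only". The protocol does not assign this outcome an analysis population.

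The SAP does. The sentence at the head of section 11.4 reads "All analyses under this section will be performed using the ITT population and also repeated with the PP population". Section 11.4 contains 11.4.1, headed as the primary safety analysis, and 11.4.3, the exploratory safety analysis of new-onset atrial fibrillation.

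SAP section 10 defines the sets:

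- **ITT:** consent in one of several forms ("full consent, abbreviated consent or waived consent and were randomized"). Dosing is not required. Grouping is by assignment: "Patients are included in the ITT population according to the treatment assigned".
- **PP:** a subset of ITT that also needs study drug, PCI and a scan at each of two times ("underwent magnetic resonance imaging (MRI) at 72 ± 24 hours and 3 months").
- **Safety:** dosed patients with at least one postdose safety assessment. The definition does not say whether grouping is by treatment received.

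Section 11.5, which goes on to adverse events, laboratory tests, vital signs and mortality, opens with "All safety analyses will be performed with the safety population". SAP section 13, on changes from the protocol, does not explain the choice of sets for the arrhythmia outcome.

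**The concern.** The arrhythmia outcome is complete at day 14, but PP membership is settled only at month 3. Between those times a patient can die, or can receive a device because of the arrhythmias being counted. The protocol's own example of a bar to CMR at entry is a device: "Known contraindication to CMR (e.g. pacemaker)". Patients with the gravest arrhythmias are therefore plausible candidates to be missing from the PP table.

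This is the first study of the drug in patients, and SAP section 9 gives safety as its main focus. Section 11.4.1 will report incidence rate ratios for each dose against placebo. A PP table that agrees with the ITT table, or looks more favourable, could be read as confirming safety when it has left out every patient who died before the late scan.

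The Safety population is defined in the SAP, yet section 11.4 does not apply it to the outcome that the protocol calls the primary safety outcome.

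**Working it through.** **1. Room for selection.** Protocol 14.1.4 plans for about 50% dropout: 80 / (1 − 0.50) = 160, which reproduces the stated enrolment. At 1:1:1:1 that is 160/4 = 40 per arm randomized and 80/4 = 20 per arm with complete data. The synopsis defines an evaluable patient by complete arrhythmia and infarct-size data. That is close to PP but not identical. If the planned loss occurs, PP could be about half of ITT.

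**2. Effect on the patient proportion (assumed inputs).** Let p be the true proportion with at least one event, and r the MRI completion of event patients relative to event-free patients. Overall completion cancels, leaving

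PP proportion = p·r / (p·r + 1 − p).

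If e is the share of all patients who had an event and missed the 3-month MRI because of it, with other missingness unrelated to events, then p·r = p − e and the formula becomes (p − e)/(1 − e).

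At p = 10%:
- e = 2%: 0.08/0.98 = 8.2%
- e = 4%: 0.06/0.96 = 6.3%
- e = 6%: 0.04/0.94 = 4.3%

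These values of e mean that 20%, 40% and 60% of event patients lose the scan because of the event. The upper end is large for a composite that includes non-sustained tachycardia.

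Over a wider range:

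| True p | r = 1 | r = 0.75 | r = 0.5 | r = 0.25 |
|---|---|---|---|---|
| 10% | 10.0% | 7.7% | 5.3% | 2.7% |
| 20% | 20.0% | 15.8% | 11.1% | 5.9% |
| 30% | 30.0% | 24.3% | 17.6% | 9.7% |

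At r = 1 there is no bias.

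**3. Effect on the comparison.** With equal loss (r = 0.5 in both arms), true proportions of 20% and 10% read 11.1% and 5.3%. Their ratio is 2.1 against a true 2.0, so both levels fall but the ratio barely moves. With unequal loss, take a true 20% in both arms, r = 0.5 on active and r = 0.75 on placebo: the ratio is 11.1/15.8 = 0.70 against a true 1.0. The comparison is materially distorted when loss differs by arm.

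**4. Metric.** These are proportions of patients, which is how the protocol defines the incidence rate. The SAP replaces that with events divided by recorded person-hours. The direction of the argument carries over but the percentages do not, because one patient with many episodes can dominate an event count.

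**5. Two further consequences.**
- Section 11.4.1 allows an optional evaluation of early arrhythmias against all-cause mortality. Repeated on PP, it contains no death before the 3-month scan.
- SAP section 12 schedules the arrhythmia analysis after the 14-day visit. PP status is unknown then for any patient who has not reached month 3, so the PP repeat cannot be completed for them at that time.

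**6. Undosed patients in ITT.** If a fraction u of active-arm person-time is undosed and runs at the placebo rate, the observed ratio is (1 − u)·RR + u. For RR = 2.0 this gives 1.98, 1.95 and 1.90 at u = 2%, 5% and 10%. For RR = 1.5 and u = 5% it gives 1.475. Person-time is recorded hours (SAP 11.4.1), and the patch goes on after study drug (Protocol 5.5.2). An undosed patient may therefore contribute no hours, and the ratio is then unchanged.

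**The case against.** The strongest reply is that ITT comes first, needs no MRI and keeps every patient who died or received a device. PP is only a supportive repeat of a descriptive outcome, and no stated decision depends on it. Clinically recognised arrhythmias are also recorded as adverse events. Those events and mortality are tabulated on the Safety population under 11.5, so serious cases in dosed patients should still be visible. All of this stands, and it limits the harm. It does not give the PP repeat a purpose for this outcome, nor does it put the patch-based rate on the Safety population.

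A reader might infer more than the documents support:

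- **That the primary analysis as a whole selects on the outcome.** It does not. The selection is confined to the PP repeat.
- **That undosed patients materially dilute the safety comparison.** They can enter ITT only, since PP requires study drug. The effect is likely negligible, and nil if they have no recording.
- **That every arm must look safer in PP.** This holds only if event patients complete the scans less often. That is plausible, but no document gives the data.
- **That a device always removes a patient from PP.** The pacemaker wording is an entry criterion. Nothing says that a device implanted later bars the 3-month scan. Death before that scan is the only certain exclusion.
- **That 11.4 and 11.5 flatly contradict each other.** Read by heading, each governs its own section. The conflict arises only if the sentence in 11.5 is taken literally for an analysis whose title labels it as safety.

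**Conclusion.** The point holds for the PP repeat of 11.4.1 and 11.4.3, which conditions a day-14 safety outcome on later survival and scan completion. The bias is downward if event patients complete the MRIs less often, and the between-arm ratio is distorted mainly if that loss differs by arm. Its size cannot be established from the documents. The figures of 8.2% to 4.3% for a true 10% rest on an assumed event proportion, an assumed event-related loss of 2% to 6% of all patients, and otherwise unrelated missingness.

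Separately, the Safety population is not named for the primary safety outcome, and the wording of 11.4 and 11.5 leaves it open whether that was intended. Neither matter touches alpha, power or sample size.

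**What to change.** In the SAP:

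1. In 11.4, exempt 11.4.1 and 11.4.3 from the PP repeat, including the optional arrhythmia–mortality evaluation. Keep PP for the CMR outcomes.
2. For 11.4.1 and 11.4.3, name the Safety population as the main set and ITT as support.
3. In section 10, add grouping by treatment received to the Safety definition. As written, the set also requires a postdose safety assessment, which the protocol's version (14.1.2) does not. State that this difference is intended, or remove it.
4. Reword the opening sentences of 11.4 and 11.5 so that only one rule applies to each safety outcome, and record the change in section 13.

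The cost is SAP wording and fewer tables. No additional data collection is needed.
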